12.4.1.1 Primary Effectiveness Endpoint

The primary effectiveness endpoint is the proportion of responders (response rate) defined as subjects with \geq 1-point improvement on the MAS Décolleté Wrinkles-At Rest from baseline to 16 weeks after last treatment as assessed by the blinded live rater.

The primary analysis will be based on a one sided binomial test at the one-sided type I error level of $\alpha = 0.025$ for the pooled data from both treatments against the null-hypothesis that the response rate is $\leq 50\%$:

H₀: R ≤50% H₁: R >50%

As further supportive explorative analyses, the effectiveness for the different time points of treatments with a 16 weeks post-treatment period in both treatment groups will be analyzed as for the primary endpoint:

- Proportion of responders (response rate) defined as subjects with ≥ 1-point improvement on the MAS Décolleté Wrinkles-At Rest from last treatment application to 16 weeks after last treatment as assessed in treatment group A.
- Proportion of responders (response rate) defined as subjects with ≥ 1-point improvement on the MAS Décolleté Wrinkles-At Rest from last treatment application to 16 weeks after last treatment as assessed in treatment group B.
- Proportion of responders (response rate) defined as subjects with ≥ 1-point improvement on the MAS Décolleté Wrinkles-At Rest from baseline to 16 weeks after first treatment as assessed in treatment group B.

In addition, two-sided 95% Wilson score confidence intervals will be provided overall, and for each treatment group in the supportive analyses.

The primary effectiveness analyses will be based on the modified FAS

Sensitivity analyses of the primary endpoint will be provided based on observed cases only and on the observed cases in the PPS.

The supportive explorative analyses will be performed on the observed cases in the modified FAS as well as on observed cases in the FAS.

12.4.1.2 Secondary Effectiveness Endpoints

One secondary effectiveness endpoint is the proportion of responders (response rate) defined as subjects with \geq 1-point improvement on the MAS Décolleté Wrinkles-Dynamic

Same

from baseline to 16 weeks after last treatment as assessed analyses as for the primary endpoint will be performed on this endpoint.

Number and percentage of subjects with any level of treatment satisfaction of the aesthetic improvement in subject's décolleté at 16 weeks after last treatment assessed by investigator and subject will be calculated and the according 2-sided 95% confidence intervals for the percentage of subjects with any level of treatment satisfaction will be provided for the pooled treatments (overall).

Number and percentage of subjects with improvement in iGAIS-Wrinkles defined in a rating of 1, 2 or 3 at 16 weeks after last treatment will be summarized and 2-sided 95% confidence intervals be provided overall. Analogous methods will be used for sGAIS-Wrinkles.

12.4.2 Safety Endpoints

All safety analyses will be performed on the SES.

AEs will be coded according to the MedDRA version in effect at the time the database is closed. Only TEAEs will be analyzed, which are defined as AEs with onset on or after date of first injection of the IMD.

12.4.2.1 Secondary Safety Endpoints

Incidences of related TEAEs will be provided by SOC and PT.

12.4.4 Special Statistical/Analytical Issues

12.4.4.1 Handling of Discontinuations and Missing Data

Missing post baseline data for the primary endpoint will be imputed according to the underlying reasons for missingness

12.4.4.2 Interim Analyses

Not applicable.

12.4.4.3 Data Monitoring Committee

Not applicable.

12.4.4.4 Multiple Comparisons/Multiplicity

The analysis of the primary effectiveness endpoint is planned to be performed on the pooled data from both treatment groups. Further tests on both treatment groups separately are to be considered as explorative supportive analyses. Therefore, the type one error rate has not to be adjusted.

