5 INVESTIGATION OBJECTIVES

Primary objectives

• To evaluate the effectiveness and safety of MRZF111 treatment for improvement of décolleté wrinkles as assessed on the MAS Décolleté Wrinkles-At Rest.

Secondary objectives

- To evaluate the effectiveness of MRZF111 treatment for improvement of décolleté wrinkles as assessed on the MAS Décolleté Wrinkles-Dynamic.
- To evaluate the subjects and physician's treatment satisfaction assessment after MRZF111 treatment of the décolleté.
- To evaluate the subjects and physician's global aesthetic improvement (GAIS-Wrinkles) after MRZF111 treatment of the décolleté.

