12.1 Determination of Sample Size

The primary effectiveness endpoint is the proportion of subjects with at least 1 point (≥ 1 point) improvement on the MAS Décolleté Wrinkles-At Rest scale at 16 weeks after last treatment compared to baseline (Day 1)

. By use of a one-sided binomial test, it will be tested at an error level of 2.5% whether the response rate is significantly larger than 50%. It is aimed to ensure a power of 90%. The binomial test is applied to the pooled data from both treatment groups.

To account for up to 10% drop-outs and potential exclusions from the FAS, a total of 112 subjects need to be enrolled in this study, i.e., 56 subjects need to be randomized to each treatment group.

Per definition, the SES will be at least as large as the FAS. Thus, according to the above outlined assumptions, at least 100 subjects will be available for safety analyses. This sample size is sufficient to observe, with a probability of 80%, at least one adverse event with actual event probability of 1.6%.

With regard to safety analyses, it should be considered that the RADIESSE[®] in its original un-diluted form is marketed since 2003. Since then, over 5 million units had been sold and used in a variety of subject populations. In this period, the majority of reported AEs were common expected injection site reactions that were mild in nature and resolved over time.

Consequently, the sample size for this study was primarily determined to ensure an adequate power for the primary effectiveness analysis, however, still providing a good probability of risk detection.

Calculations to determine the required sample size were performed using the software nQuery Version 8.1.2.0, Statistical Solutions Ltd. 2017, and validated by double programming with proc power on SAS 9.4, SAS Institute Inc., Cary, NC, USA, 2016.

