7.1 Effectiveness Endpoints

The primary and secondary effectiveness endpoints will be summarized using the modified FAS population with missing data replaced as described in Section 7.4.1; for sensitivity purposes, these analyses will also be performed on the modified FAS with observed data and on the PPS. [REDACTED]

Statistical tests will be one-sided binomial tests at error level 2.5% for the responder rates in general. Adequate [REDACTED] statistics will be provided for each variable for the pooled data and by realized treatment group. The supportive exploratory analyses for the primary effectiveness endpoint will also be performed on the observed cases in the FAS. Metric variables will be summarized by number of observations (Nobs), number of missing values (nmiss), mean, standard deviation, median, minimum, Q1, Q3 and maximum. Categorical variables will be summarized by number and rate of events per category where the denominator will be chosen according to the adequate analysis population. Ordered categorical data may be summarized by metric and categorical statistics. All variables will be analyzed as absolute data and as change from baseline, as applicable.

Summary statistics for all visits and changes from baseline for all post-baseline visits will be displayed for each effectiveness endpoint for each treatment group and the pooled data.

If not otherwise specified, confidence intervals in the following refer to the two-sided 95% Wilson score confidence intervals.

All data captured in the electronic Case Report Form (eCRF) will be listed.

P-values will be reported to four decimal places (e.g., $p=0.0375$). P-values below 0.0001 will be presented as ' <0.0001 '.

Mean, median, and standard deviation will be reported to one decimal place more than the data were collected; for derived data, an adequate number of decimal places will be chosen. Percentages will be calculated using the denominator of all subjects in a specified population or treatment group. The denominator will be specified in a footnote to the tables for clarification if necessary. Percentages will be reported to one decimal place.

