7.1.1 Primary Effectiveness Endpoint(s)

The primary effectiveness endpoint is the proportion of responders (responder rate) defined as subjects with ≥ 1 -point improvement on the MAS 'Décolleté Wrinkles – At Rest' from baseline to 16 weeks after last treatment as assessed [REDACTED].

The primary analysis will be based on a one-sided binomial test at the one-sided type I error level of $\alpha = 0.025$ for the pooled data from both treatments against the null-hypothesis that the response rate (R) is $\leq 50\%$:

$$H_0 : R \leq 50\%$$

$$H_1 : R > 50\%.$$

H_0 is rejected if the resulting one-sided p-value is <0.025 and the observed proportion of responders is >0.5 .

As further supportive explorative analyses, the effectiveness for the different time points of treatments with a 16 weeks post-treatment period in both treatment groups will be analyzed as for the primary endpoint:

- Proportion of responders (response rate) defined as subjects with ≥ 1 -point improvement on the 'MAS Décolleté Wrinkles – At Rest' from last treatment application to 16 weeks after last treatment as assessed [REDACTED].
- Proportion of responders (response rate) defined as subjects with ≥ 1 -point improvement on the MAS 'Décolleté Wrinkles – At Rest' from last treatment application to 16 weeks after last treatment as assessed [REDACTED].
- Proportion of responders (response rate) defined as subjects with ≥ 1 -point improvement on the MAS 'Décolleté Wrinkles – At Rest' from baseline to 16 weeks after first treatment as assessed [REDACTED].

In addition, two-sided 95% Wilson score confidence intervals for response rates will be provided overall, and for each treatment group in the supportive analyses. A similar SAS code as given above will be used.

The primary effectiveness analyses will be based on the modified FAS with missing data replaced by a multiple imputation approach for each realized treatment group.

Sensitivity analyses of the primary endpoint will be provided based on observed cases only in the modified FAS and on the observed cases in the PPS. The supportive explorative analyses will be performed on the observed cases in the modified FAS as well as on observed cases in the FAS. For analysis based on observed data, SAS code similar to the following will be used:

```
proc freq data = dataset order = freq;  
  tables response / binomial (level="1" wilson p=.5) cl alpha=.05;  
run;
```

, assuming the response is coded with '1' and no response is coded with '0'.

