7.1.2 Secondary Effectiveness Endpoints

MAS ratings

One secondary effectiveness endpoint is the proportion of responders (response rate) defined as subjects with \geq 1-point improvement on the MAS 'Décolleté Wrinkles – Dynamic' from baseline to 16 weeks after last treatment as assessed [REDACTED]. Same analyses as for the primary endpoint will be performed on this endpoint (including sensitivity and supportive exploratory analyses on the same analysis sets and treatment groups).

Satisfaction with décolleté appearance

[figure not shown]
Number and percentage (n, %) of subjects with treatment satisfaction defined by a level of 1, 2 or 3 will be summarized and the corresponding two-sided 95% confidence intervals will be provided for the pooled treatment groups (overall).

[figure not shown]
GAIS

[figure not shown]
Number and percentage (n, %) of subjects with "improvement" in iGAIS-Wrinkles defined as a rating of 1, 2 or 3 at 16 weeks after last treatment will be summarized and two-sided 95% confidence intervals will be provided for the pooled treatment groups. Analogous methods will be used for sGAIS-Wrinkles.

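### The secondary MAS-Dynamic test at one-sided 2.5% is not tied to the primary result, and the Protocol's reason for making no alpha adjustment does not cover it

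*Protocol*

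**What the plan says.** The plan has one primary endpoint, the response rate on MAS At Rest at 16 weeks after last treatment. Protocol 12.1 specifies a one-sided 2.5% test against 50% and adds: "The binomial test is applied to the pooled data from both treatment groups". Under SAP 7.1.1 the null hypothesis is "rejected if the resulting one-sided p-value is <0.025", provided the observed rate also exceeds one half.

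The response rate on MAS-Dynamic is a secondary endpoint. Among the secondary objectives, Protocol section 5 lists: "To evaluate the effectiveness of MRZF111 treatment for improvement of décolleté wrinkles as assessed on the MAS Décolleté Wrinkles-Dynamic". For its analysis SAP 7.1.2 says: "Same analyses as for the primary endpoint will be performed on this endpoint". Protocol 12.4.1.2 has the same instruction ("analyses as for the primary endpoint will be performed on this endpoint"). SAP 7.1 sets the level: "Statistical tests will be one-sided binomial tests at error level 2.5% for the responder rates in general". The paragraphs on the other secondary endpoints (satisfaction and GAIS-Wrinkles) name only counts, percentages and confidence intervals.

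On multiplicity, Protocol 12.4.4.4 gives two premises, a pooled primary analysis and exploratory status for the tests within each treatment group, and concludes: "Therefore, the type one error rate has not to be adjusted". SAP 7.4.4 reaches the same conclusion, but the text before it is blacked out.

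**The concern.** The pooled Dynamic test is neither the primary test nor a by-group test, so neither premise in Protocol 12.4.4.4 applies to it. Both documents use the word exploratory where they intend it. SAP 7.1.2 lists the sensitivity and supportive exploratory analyses as included in what is repeated for Dynamic, which leaves the main pooled Dynamic test without that label. Nothing visible makes it wait for the primary.

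As written, Dynamic could be reported as significantly above 50% after At Rest has failed, and the plan does not say what that result would mean. If it were presented as evidence of effectiveness, there would be two unlinked routes to a claim at 2.5% each. If it is not meant that way, the plan should say so before the results are known.

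**Working it through.** **Inputs.** Level 0.025 one-sided for each test and null rate 50% (Protocol 12.1; SAP 7.1 and 7.1.1). Total N is 112 with 10% allowed for losses (Protocol 12.1). The correlation between the two test statistics is not in the documents, so it is an assumption and a range is shown.

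**The plan's own figures.** 100 / 0.90 = 111.1, rounded up to 112, which agrees with the stated total. The safety statement also reproduces: 1 − (1 − 0.016)^100 = 80.07%. The plan gives no family-wise error figure to reproduce.

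**Nominal error over the two tests, both true rates 50%.**
- Upper bound: 0.025 + 0.025 = 5.00%.
- Independent tests: 1 − (1 − 0.025)² = 4.94%.
- Correlated tests: 1 − P(Z1 < 1.96, Z2 < 1.96) for a bivariate normal with correlation ρ.

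| ρ | At least one false rejection |
|---|---|
| 0 | 4.94% |
| 0.5 | 4.54% |
| 0.7 | 4.17% |
| 0.8 | 3.90% |
| 0.9 | 3.52% |
| 1 | 2.50% |

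**Effect of the form of the test.** The binomial distribution is discrete, so the actual size differs from 2.5%. The columns below use the correlation between the two binary responses within a subject and assume complete data; imputation is not modelled.

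| Rule | Size of one test | Pair, correlation 0 | Pair, 0.5 | Pair, 0.7 |
|---|---|---|---|---|
| Exact, n = 100, at least 61 responders | 1.76% | 3.49% | 3.24% | 2.98% |
| Exact, n = 112, at least 67 | 2.34% | 4.62% | 4.25% | 3.91% |
| Normal approximation, n = 100, at least 60 | 2.84% | 5.61% | 5.13% | 4.71% |

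The third row is included because the observed-case code in SAP 7.1.1 requests a binomial analysis without an exact option. With 60 of 100 responders, z = (0.60 − 0.50) / √(0.25/100) = 2.00, which exceeds 1.96.

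**Under a fixed sequence.** If the At Rest null is true, any false claim requires At Rest to reject, which has nominal probability at most 2.5%. If only the Dynamic null is true, a false claim requires Dynamic to reject, again at most 2.5%. The nominal family-wise error is therefore at most 2.5% at any correlation.

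**The case against.** The strongest reply is that nothing in the plan is breached. There is a single primary endpoint, and sample size and power rest on it alone. The 2.5% is stated for that test and as a per-test level for response rates. Neither document claims family-wise control across primary and secondary endpoints, or says that success on either one counts as trial success. Dynamic is called secondary throughout. All of this stands, and it limits the point to the undefined status of one test.

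A reader might infer that the primary's error rate is inflated. It is not: adding a Dynamic test does not change the probability that At Rest rejects.

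A reader might also infer that the two tests run at 4 to 5% as a matter of fact. The documents do not support that. The figure applies only if Dynamic is read as a claim and both true rates are 50%, and it depends on an unstated correlation. Two scales for the same area, in the same subjects at the same time point, may well be highly correlated, and the nominal figure then falls towards 2.5%.

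Finally, a reader might infer that the SAP gives no reason covering Dynamic. Its reason is redacted, and Protocol section 12 leaves further statistical detail to the SAP, so criticism of the reasoning must stop at the Protocol. The redaction does not remove the point, because the visible rules still set a 2.5% test for Dynamic, no visible order and no adjustment.

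**Conclusion.** The concern holds in limited form. A secondary endpoint receives the primary's formal test with no visible link to the primary result, and the reason in Protocol 12.4.4.4 does not reach it. The primary conclusion is not at risk.

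The consequence is conditional on a significant Dynamic result being treated as an effectiveness claim. For non-negative correlation the nominal chance of at least one false claim then lies between 2.5% and 4.94%, with 5% as the bound under any dependence. Actual sizes shift with the form of the test: the exact test at n = 100 stays at or below about 3.5% under non-negative correlation, while the normal approximation can go somewhat above the nominal figures. This is worth correcting because the remedy is short and leaves the primary analysis unchanged.

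**What to change.** In Protocol 12.4.4.4 and SAP 7.4.4, state a fixed sequence:

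1. Test pooled MAS At Rest at one-sided 2.5%.
2. Only if step 1 rejects, test pooled MAS-Dynamic at one-sided 2.5%.

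If the sponsor wants no formal Dynamic claim, one sentence labelling the Dynamic test as supportive closes the gap equally well. The by-group and supportive tests are already labelled exploratory and need no change. If the redacted text in SAP 7.4.4 already settles Dynamic's status, it is enough to bring the Protocol into line with it.

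The cost is a short paragraph in each document, to be settled before database close. N, the primary's alpha and its power are unchanged. The downside of the sequence is that no formal Dynamic claim is possible if At Rest fails.

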13 DATA HANDLING AND RECORDKEEPING

By signing and dating the eCRF, the delegated investigator will confirm that all investigations have been completed and conducted in compliance with the CIP, and that reliable and complete data have been entered into the eCRF.

13.1 Corrections to Data

All data required by this CIP are to be entered into a validated database of eCRFs. However, unless otherwise specified in Section 11.2, direct entries are not allowed; data must be transcribed from the source (e.g., subject file) to the eCRF.

If corrections in subject scales or assessments are necessary, the subject should be instructed to make a correction by drawing only a single line through the error, leaving the incorrect entry legible. The subject should date and sign the correction. The investigator should not make any changes to these documents. The data management/biostatistics vendor (Metronomia Clinical Research GmbH) will be responsible for data processing. Database close will occur only after quality assurance procedures have been completed.

13.2 Recordkeeping

Essential documents should be retained for at least 15 years after the last date of manufacture. These documents should be retained for a longer period, however, if required by applicable regulatory requirements or by agreement with the sponsor.

The sponsor and principal investigator shall take measures to prevent accidental or premature destruction of these documents. The principal investigator or sponsor may transfer custody of records to another person/party and document the transfer at the investigation site or at the sponsor's facility.

Essential documents at the investigation site include (among other documents):

- Source documentation (e.g. subject files, medical records, subject, investigator and questionnaires).
- Subject identification code list (i.e., provided by template to the investigator, along with the Investigator Site File, at the beginning of the investigation), which identifies the subject by number, name, and date of birth.
- A signed copy of the final CIP and any amendment.
- CD/DVD/USB with eCRF data, data clarification forms, and any associated subjectrelated source data or, where applicable, authorized copies of source data).
- Signed informed consent forms.
- Copies of site investigators' and co-workers' curricula vitae.
- Copies of all direct correspondence with the EC and with the regulatory authority (ies).

- Copies of IMD receipt forms and device inventory forms.
- Copies of all relevant correspondence between the investigator and the monitor, and between the investigator and the sponsor.
- Copies of safety information reported during the investigation and submitted by the sponsor.

13.3 Destruction of Investigation Documents

Investigation documents may not be destroyed by investigation site personnel prior to the retention period specified above without the prior written consent of the sponsor. The party who signed the investigator contract must inform the sponsor in due time if the principal investigator leaves the institution during the retention period. This rule also applies when the institution closes within the retention period.

14 PUBLICATION POLICY

The investigational results should be published in the public domain, and publishing details will be given in the clinical study agreement. Publications concerning investigational results must be approved in advance by the sponsor in writing.

The results of this investigation and any discoveries related to this investigation, regardless of whether they have technical or medical character, are the property of the sponsor.

16 APPENDICES

1 LIST OF ABBREVIATIONS

AE	Adverse event
ADE	Adverse device effect
ATC	Anatomical Therapeutic Chemical classification system of the World Health Organization
BMI	Body Mass Index
CRO	Contract research organization
DRM	Data review meeting
eCRF	Electronic case report form
FAS	Full analysis set
G	Gauge
GAIS	Global Aesthetic Improvement Scale
iGAIS	Investigator's Global Aesthetic Improvement Scale
IMD	Investigational medical device
LOCF	Last Observation Carried Forward
MAS	Merz Aesthetic Scale
MedDRA	Medical Dictionary for Regulatory Activities
MI	Multiple Imputation
Nobs	Number of observations
pdf	Portable data format
PPS	Per protocol set
PT	Preferred term
SAE	Serious adverse event
SAP	Statistical analysis plan
SES	Safety evaluation set
sGAIS	Subject's Global Aesthetic Improvement Scale
SOC	System organ class
TEAE	Treatment emergent adverse event
TFLs	Tables, Figures, and Listings
WHO-DD	World Health Organization Drug Dictionary

